**Table 1. Study visit schedule, and sample collection.**

The table presents the maximal number of visits and calls for a participant enrolled early during the first RSV season (2016-2017) who will have up to 48 months of follow-up. As a result of the variable duration of follow-up not all participants will have the V4-V5 visits, or phone calls (see also **Figure 7**: study timeline).

RZ: Enrollment and randomization visit, V: clinic visit, PC: Phone-call.

See Section O (SPECIAL STUDY PROCEDURES AND TECHNIQUES) for the specifics of studies that will be performed on the biological samples.

a Complete physical exam during the randomization visit, then brief physical exams during the following clinic visits. b Nasal wash, blood, and stool will be obtained at V3 visit only for the year three recruits as they won't be in the study long enough for a V4 and V5 visits. c Nasal wash, blood, and stool will be obtained at V4 visit for the year one and year two recruits. If for some reason the year one recruits are not able to provide the designated samples at V4 visit, we may obtain these samples at their V5 visit with parent permission. The samples that are listed to be obtained at V4 will be obtained at V5 ONLY if they were not obtained at V4 (applicable to participants who will be recruited at the 1st year of the study). In any case, each participant will contribute only one set of samples at the V3-V5 visits.

DNA sample will be obtained from blood sample, unless the parent doesn't agree to blood draw: in this case DNA sample will be obtained by a buccal swab.

If blood is to be obtained at enrollment or a scheduled study visit, but parent opts out of blood draw at that time, this blood may be drawn at a future visit with parent permission.

### 1. Enrollment and Randomization visit (RZ) during the acute hospitalization:

- a. Eligibility determined based upon inclusion and exclusion criteria.
- b. Informed consent obtained.
- c. Release of medical data obtained.
- d. Provide an information brochure about the study (will include study ID, contact phone number of the investigators, instruction to avoid any macrolide antibiotic during the 2 weeks of study therapies). A copy of this brochure will be send to the primary care physician.
- e. Detailed family history and environmental allergy questionnaires obtained.
- f. Medical history obtained.
- g. Study physical examination including height and weight performed. This physical exam is performed to assure the child can participate in the study. **This exam has different goals than the physical exam performed by the child's attending physician as a standard of care, and cannot replace the attending's exam.**
- h. Document the administration over the past 24 hrs of: supplemental oxygen, IV fluids, albuterol or other bronchodilators, antibiotics.
- i. Calculate bronchiolitis severity score.
- j. Provide education about study medications, and discuss the need to avoid any macrolide antibiotic during the active phase of the study.
- k. Provide and teach Study Medication Diary (This paper diary monitor for study medications adherence and potential side effects) completion.
- l. Obtain baseline blood, stool, nasal wash and nasal brush samples, and urine (if able to obtain while child is hospitalized).
- m. Dispense first batch of study medications and dosing syringes. Teach study medication administration.
- n. Coordinate study medication delivery with the nursing staff of the inpatient unit.
- o. Schedule the clinic follow up visit (V1).
- p. Obtain contact information (including e-mail if available) and preferred time for follow up telephone calls (PCs).
- q. Provide/arrange for parent's compensation.
- r. If a Respiratory Pathogen Multiplex PCR testing has been performed in SLCH, document the presence of other respiratory viruses (if not done, this will be performed at the end of the RSV season on a nasal wash sample).

### 2. Daily follow up during the acute hospitalization (HSP1, HSP2 etc...):

- a. Review Study Medication Diary card.
- b. Review study medication treatment and adherence.
- c. Remind date of clinic follow up visit (V1) and the need to bring study medication bottle to the visit. Dispense materials for collection of stool sample before the V1 visit.
- d. At the end of hospitalization document the following: supplemental oxygen (days), IV fluids (days), albuterol or other bronchodilators, hypertonic saline inhalations, antibiotics, oral steroids, inhaled steroids, montelukast, length of hospitalization (days).
- e. Schedule the date for the MED1 phone call and the date/time for the delivery of the second bottle of study medications (for the 2nd week 2 of the study treatment).

**3. A weekly phone call during the 2 weeks of active treatment phase of the study (MED 1, MED2):**

- a. Review Study Medication Diary card (monitor medications adherence and potential adverse reactions).
- b. Confirm date/time for delivery of second bottle of study medication (during week one only).
- c. Schedule the date for the MED2 phone call (during week one only).
- d. Remind date of follow up visit (V1) and the need to bring study medication bottle to the visit. Remind the procedures for collection of stool sample before V1 visit.
- e. Answer families questions regarding study medications and study visits.

**4. Clinic visit: V1: 14 days after randomization (day 15 with a window of  $\pm$  3 days):**

If the family absolutely cannot attend the clinic visit, a phone call will be conducted in lieu of the clinic visit to collect clinical outcomes.

- a. Brief history (including drug adverse reactions) and partial physical exam aiming to exclude (or document) the presence of wheezing on lung exam.
- b. Review and collect Study Medication Diary card.
- c. Document adherence to study medications by the Study Medication Diary. Weigh study medication bottles.
- d. Obtain blood, nasal wash and brush samples, and urine (if able to obtain while child is at V1).
- e. Collect stool sample that was obtained before the visit. If a stool sample could not be collected before/during the visit, it will be shipped to the investigators by a courier.
- f. Review any unanticipated change in medical status-if needed, document this change in the AE or SAE form and report accordingly.
- g. Review contact information and schedule PC1
- h. Provide parent's compensation.

**5. Follow up telephone calls (PC): 2 months after enrolment, and then every 2 months (these phone calls have a window of  $\pm$  3 weeks):**

- a. Monitor for the following since the last visit/ telephone call\*:

1. Symptoms of wheezing (with and without a cold), use of rescue albuterol, use of oral corticosteroids, ED /unscheduled office visits, hospitalizations for respiratory symptoms, parental absence from work due to child's respiratory illnesses.
2. Physician diagnosis of asthma
3. Use of antibiotics, inhaled steroids, montelukast.
4. Change in pet exposure, day care status, and cigarette smoke exposure.
5. Any unanticipated change in medical status-if needed, document this change in the AE or SAE form and report accordingly.
6. Review contact information and obtain as many options for additional contact options.
7. Schedule the next PC.
8. Mail parent's compensation.

\*For PC1 only: time frame for measurements of clinical outcomes is starting at the end of study treatments (2 weeks from randomization=V1).

**6. Yearly clinic visits (V2-V5): The first yearly visit will be conducted 6 months after randomization, and then every 12 months (these yearly visits have a time window of  $\pm 1$  month):**

Participants recruited early during the first RSV season (2016-2017) may have up to 4 yearly visits (V2-V5). Participants recruited late during the last RSV season (2018-2019) may have only one yearly visits (V2). If any of these visits would be conducted within the time frame of any of the PC phone calls, then the information from this visit will be recorded in lieu of the phone call data. However, if the family absolutely cannot attend the yearly clinic visit (e.g., left the St. Louis metro area), a phone call will be conducted in lieu of the clinic visits to collect clinical outcomes.

- a. Partial physical exam (including weight and height).
- b. Monitor for the following since the last telephone call:
  1. Symptoms of wheezing (with and without cold), use of rescue albuterol, use of oral corticosteroids, ED /unscheduled office visits, hospitalizations for respiratory symptoms, parental absence from work due to child's respiratory illnesses.
  2. Physician diagnosis of asthma
  3. Use of antibiotics, inhaled steroids, montelukast.
  4. Change in pets exposure, day care status, cigarette smoke exposure.
  5. Any unanticipated change in medical status-if needed, document this change in the AE or SAE form and report accordingly.
- c. Obtain nasal wash sample (V2 and V4 or last visit (V3) for year 3 recruits).
  1. If the COVID-19 virus is still circulating in the St. Louis region at the time of the child's last nasal wash collection (V4 or last visit (V3) for year 3 recruits), we may not obtain this nasal wash sample to prevent undue risk of contamination to the child of contracting COVID-19.

- d. Obtain nasal brush sample (V2 only).
- e. Collect stool sample that was obtained at home (V2 and V4 or last visit (V3) for year 3 recruits).
- f. Obtain blood for (V4, or last study visit (V3); for participants enrolled in year 3 who will not have V4):
  - 1. Specific IgEs (inhalant allergens- see #7 at the list of secondary outcomes below): Specific IgEs will be performed at V4 or at the last study visit (V3) for year 3 recruits. Serum from the other yearly visits will be saved and may be used for allergy testing at a later time.
  - 2. Eosinophil Count, Total IgE: V4 or last visit (V3) for year 3 recruits.
  - 3. We may obtain COVID-19 antibody testing with parent permission: V5, V4 or last visit (V3) for year 3 recruits.
- g. Review contact information and obtain as many options for additional contact options.
- h. Schedule the next PC.
- i. Provide parent's compensation.

**7. Extended Observation Follow up telephone calls (PC): Extended observation calls will start following the participants final phone call from their initial enrollment observation period and will occur every 4 months (these phone calls have a window of  $\pm$  6 weeks):**

- a. Monitor for the following since the last visit/ telephone call\*:
  - 1. Symptoms of wheezing (with and without a cold), use of rescue albuterol, use of oral corticosteroids, ED/unscheduled office visits, hospitalizations for respiratory symptoms, parental absence from work due to child's respiratory illnesses.
  - 2. Physician diagnosis of asthma
  - 3. Use of antibiotics, inhaled steroids, montelukast.
  - 4. Change in pet exposure, day care status, and cigarette smoke exposure.
  - 5. Any unanticipated change in medical status-if needed, document this change in the SAE form and report accordingly.
  - 6. Review contact information and obtain as many options for additional contact options.
  - 7. Schedule the next PC.
  - 8. Mail parent's compensation.

## **F. OUTCOME VARIABLES**

### **1. PRIMARY OUTCOME MEASURES**

- a. Clinical trial outcome: The occurrence of a third episode of post-RSV wheezing measured over a follow up duration of 18-48 months, quantified by a Cox proportional hazards regression model, and compared between the groups.

*Primary outcome assessment:* Episode of wheezing will be detected by the question “Has your child’s chest sounded wheezy or whistling (with and without a cold)? This question was adopted from the International Study of Asthma and Allergies in Childhood (ISAAC) study, and was previously utilized in our pilot APW-RSV study and in the RBEL study. Data collection will be conducted in a standardized way, during study visits and phone calls, utilizing Data Collection Forms that have been modified from our APW-RSV study and in the RBEL study.

*Definition of a new distinct wheezing event vs. continuation of previous wheezing symptoms:* In order to define a new wheezing episode a child should not wheeze for at least 7 days before the new event. If the time frame from the previous wheezing episode (last time that the child wheezed) to the onset of wheezing symptoms is shorter than 7 days, these wheezing symptoms would be attributed to the previous wheezing episode and will not be counted as a new event. This approach was utilized in our previous pilot APW-RSV study.

*Time frame for primary outcome assessment:* For the purpose of this study, wheezing detected during the initial RSV bronchiolitis will not be included in the count of post-RSV wheezing. The time frame for measurement of post-RSV wheezing (and other long-term outcomes) starts at the end of the treatment period (2 weeks after randomization) and ends at end of the follow-up period. Therefore, a wheezing episode that occurs at the first 2 weeks of the study, does not “count” toward the outcome of RW.

- b. Microbiome study outcome: Upper airway microbiome community structure measured at the end of study treatments, and its relationship with the occurrence of post-RSV RW ( $\geq 3$  episodes).

See the analysis plan for details on the analytic approach of the microbiome studies.

## 2. SECONDARY OUTCOME VARIABLES MEASURED DURING THE FOLLOW-UP PERIOD (18-48 MONTHS):

- a. Time to physician asthma diagnosis.
- b. Time to asthma diagnosis OR to the third episode of wheezing.
- c. Annualized number of days with: any respiratory symptoms (wheezing, cough, or shortness of breath), or albuterol use.
- d. Rate of oral corticosteroid courses use.
- e. Rate of antibiotic courses use.
- f. Rates of drug related side effects and severe adverse reactions.

Secondary clinical outcomes (including the outcomes listed in #3 below) will be assessed by clinic visits and phone call interviews as described for the primary outcome. These will be measured as we previously described.

The monitoring of potential drug related side effects will start immediately after randomization. The time frame for measurement of all other long-term outcomes starts at the end of the treatment period (2 weeks from randomization) and ends at end of the follow-up period.

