### **B. SECONDARY AND EXPLORATORY HYPOTHESES:**

In infants hospitalized with RSV bronchiolitis, azithromycin therapy (compared to placebo) will result in:

1. Decreased nasal lavage levels of IL-8, neutrophil elastase, and matrix metalloproteinase-9 (MMP-9) measured on day 15 after randomization.
2. Not different rates of upper airway colonization with macrolide-resistant bacteria measured at the end of study treatments (day 15 after randomization) and at the 6-months clinic visit.
3. Not different incidence of treatment-related adverse reactions.
4. Reduced likelihood and longer time to develop 4th wheezing episode.
5. Reduced likelihood and longer time to develop physician asthma diagnosis.

6. Fewer annualized days with: a) wheezing, b) any respiratory symptoms, c) use of rescue albuterol, d) antibiotic use, e) oral corticosteroid use, f) parental absence from work and infant absence from day care, and g) nights with awakening due to respiratory symptoms.
7. Lower rates of: a) oral corticosteroid use, b) antibiotic courses, c) ED and urgent care visits, d) hospitalizations for respiratory symptoms, f) upper respiratory infections.
8. Smaller proportion of children: a) who were prescribed asthma controllers medications: ICS and/or montelukast, b) who developed RW, c) have physician asthma diagnosis.
9. Lower cumulative number of subsequent wheezing episodes.
10. Lower mean total IgE level and eosinophil counts measured at yearly follow up visits.
11. Smaller proportion of children with at least one positive specific IgE (SigE) to inhalant allergens measured at the first and last yearly follow up visit.
12. Modifications of the viral and/or the fungal components of the airway microbiome, which are related to the occurrence of post-RSV RW.

[figure not shown]

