## P. POTENTIAL RISKS

Potential risks include potential adverse effect of azithromycin, study burden from phone calls and clinic visits, pain and discomfort from blood testing, and mild discomfort from nasal wash and/or brush collection. Participants will be reimbursed for time and travel costs limiting financial burden

It is expected that some of the children participating in this study will experience worsening of their RSV bronchiolitis, and will require intensive care management. In addition, it is expected that most study participants will develop wheezing episodes and asthma and some may require hospitalization. These are expected outcomes during/following RSV bronchiolitis and likely to occur even if the child will not participate in the study. See the "Protection Against Risks" Section for description of the management of these events

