**A. DATA AND SAFETY MONITORING BOARD (DSMB)**

The DSMB that will monitor this project will be convened by the NHLBI. In brief, the DSMB will review safety data, study conduct, data management, and analysis/interpretation. To do so, the DSMB will be asked to review the protocol, informed consent form/process, protocol amendments, data on recruitment and retention, protocol adherence, safety events, any emerging information impacting the safety or ethics of study participation, and manuscripts. A DSMB charter will be approved by the DSMB and will include a detailed description of the DSMB membership, responsibilities, and policies. DSMB reviews will occur at least yearly, and more frequently if warranted as described in the DSMB Charter. Recommendations (minutes/reports) from the DSMB will be provided to the Principal Investigator (PI), [name], and NHLBI Program Official from the DSMB. The PI will distribute the Minutes to the IRB.

**B. SAFETY REPORTING: COLLECTION AND REPORTING OF ADVERSE EVENTS AND SERIOUS ADVERSE EVENTS*****B.1. Definitions: Adverse events, serious adverse events and unanticipated problems:***

**Adverse Event (AE)**- Any untoward medical occurrence associated with the use of a drug in humans, whether or not considered drug related. An adverse event can also be any unfavorable and unintended sign (e.g., an abnormal laboratory finding), symptom, or disease temporally associated with the use of a drug, without any judgment about causality. Determination of the relationship between the event and study drug, or a study mandated procedure must be made by the PI. This definition will also include changes in the medical status that may be related to study procedures. All adverse events will be categorized as being possibly, probably, definitely, or not related to study drug.

**Serious Adverse Event (SAE)** - An adverse event is considered "serious" if, it results in any of the following outcomes:

1. Death
2. A life-threatening adverse reaction
3. Hospitalization or prolongation of existing hospitalization
4. A persistent or significant disability interfering with the ability to conduct normal life functions.

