#### Determining AE relatedness:

The PI will determine if an AE is "possibly related", "probably related", "definitely related", or "not related" to the study drug or a study mandated procedure. The determination will be based on the biologic plausibility, the temporal relationship, and the presence or absence of an alternative explanation for an AE. This protocol requires up to 47 months of follow up after a 14 day treatment period (with either azithromycin or placebo). Given even in the case of active drug (azithromycin), the drug will be cleared within 15 days ( $T_{1/2} = 68 \text{ hours} \times 5 = 340 \text{ hours}$  or 14.2 days), *study related* risks during the final 47 months of follow up will be from study procedures/monitoring or long term effects of prior drug exposure (e.g., a future allergic reaction). Therefore the timing of an adverse event will have a significant role in the determination of relatedness.

AEs will be categorized as having one of the following causalities:

- Not Related: The AE is clearly not related to the study drug.
- Possibly Related: The AE follows a reasonable, temporal sequence with administration of the study drug and/or follows a known response pattern to treatment with the study drug but could readily have been produced by the subject's clinical state, environmental factors, or other modes of therapy or concomitant drugs administered to the subject.
- Probably Related: The AE is uncommon in the subject population and follows a reasonable, temporal sequence from administration of study drug; follows a known response pattern to treatment with the study drug; and is not likely to have been produced by the subject's clinical state, environmental factors, or other modes of therapy or concomitant drugs administered to the subject.
- Definitely Related: The AE is uncommon in the subject population and follows a reasonable, temporal sequence from administration of study drug; follows a known response pattern to treatment with the study

drug; and cannot have been produced by the subject's clinical state, environmental factors, or other modes of therapy or concomitant drugs administered to the subject.

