- a. Demographic: Sex, age, race.
- b. Baseline asthma/allergy phenotypic characteristics: Personal history of eczema, parental history of asthma, peripheral eosinophil count on enrolment.
- c. Environmental phenotypic characteristics: second hand smoking, pet exposure.
- d. Acute bronchiolitis characteristics: Duration of respiratory symptoms before enrolment, and the presence of co-infection with other respiratory viruses during the RSV bronchiolitis (e.g. rhinovirus).

\*The following covariates will be compared between the groups and would be considered to be included in the Cox models:

- a. Age at enrollment (months)
- b. Gender
- c. Race
- d. Birth weight
- e. Length of pregnancy (wks)
- f. Maternal smoking status during pregnancy
- g. Breast feeding status at the time of enrollment

- h. Tobacco smoke exposure (at the time of enrollment and during f/u visits)
- i. Pet exposure (at the time of enrollment and during f/u visits)
- j. History of eczema
- k. Parental history of asthma
- l. Duration of respiratory symptoms prior to randomization
- m. Duration of hospitalization (hours: measured from the time of the Emergency Room visit that triggered the admission and until time of discharge)
- n. Lowest O2 saturation recorded on room air
- o. Antibiotics use during the acute hospitalization. Antibiotic use during the follow up period will be measured as one of the secondary outcomes.
- p. Co-infection with other respiratory virus on enrollment (mainly Rhinovirus)
- q. Complete compliance with study medication (defined as >80% compliance)
- r. Antipyretic (acetaminophen and Ibuprofen) use during the initial RSV bronchiolitis
- s. Day care attendance
- t. Number of siblings in the house
- u. Eosinophil count at enrollment

**Censoring considerations:** All subjects will be censored at the time of the last contact with the subject confirms that they had not experienced the outcome measure. This applies whether the subject is a dropout or has remained on study until the end.

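### The clinical safety outcome counts only events attributed to study drug, and no between-arm comparison of all adverse events is pre-specified, including respiratory worsening in days 1-14

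*Combined protocol and SAP*

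**What the plan says.** **Outcome and hypothesis.** Section V.F.2 lists one clinical safety outcome, item f: "Rates of drug related side effects and severe adverse reactions". Section III.B, item 3, predicts "Not different incidence of treatment-related adverse reactions", with no margin. Macrolide resistance is a separate laboratory outcome (V.F.4).

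**Attribution.** Section VI.B.1 states: "Determination of the relationship between the event and study drug, or a study mandated procedure must be made by the PI". Section VI.B.2 gives the task to the investigator in one place and to the PI in another. Of the three related grades, the upper two carry a rarity condition: "Probably Related: The AE is uncommon in the subject population and follows a reasonable, temporal sequence from administration of study drug" and "Definitely Related: The AE is uncommon in the subject population and follows a reasonable, temporal sequence from administration of study drug". *Possibly related* has no such condition. The plan does not say which grades make an event drug related for item f.

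**Collection.** All AEs and SAEs are collected from enrollment to Phone Call 1 at two months, whatever their cause (VI.B.2, Reporting period). Prolonged hospitalization is an SAE (VI.B.1).

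**Days 1-14.** Section V.P expects that some infants "will experience worsening of their RSV bronchiolitis, and will require intensive care management". Drug side effects are monitored from randomization. The recurrent-wheeze count and all other long-term outcomes start at the end of treatment (V.F.1, V.F.2).

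**Hospital course.** Oxygen days, IV fluid days and length of stay are recorded at discharge (V.E.2, daily follow-up, item d). None is an outcome. Length of stay reappears in VII.A as candidate covariate m: "Duration of hospitalization (hours: measured from the time of the Emergency Room visit", running to discharge.

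**Analysis.** Section VII.A gives no method for comparing adverse events between arms, whether all-cause or attributed.

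**The concern.** These infants take study drug while acutely ill. The early harms one would most want to exclude (respiratory deterioration, a longer stay, gastrointestinal illness) are also what the illness produces. For a single child, a blinded investigator can reasonably ascribe such an event to the bronchiolitis. Only the comparison of randomised groups can show whether there were more of them on azithromycin.

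Item f applies the individual judgment first and counts afterwards. An excess spread over events each judged unrelated would not enter the safety result, and the wheeze outcomes begin too late to show it. The trial could then report no difference in treatment-related reactions for a drug it hopes to see used widely in hospitalized infants, without having reported the comparison that randomisation makes possible.

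**Working it through.** The documents give no expected rate, margin or power for safety, so there is no stated figure to reproduce. The check has three parts.

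**1. Where an early event could appear in the results**

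| Event in days 1-14 | Collected? | Pre-specified between-arm analysis |
|---|---|---|
| AE or SAE judged related | Yes | Named as outcome f; no method given |
| AE or SAE judged not related | Yes | None |
| Wheeze, respiratory hospitalization | As AE/SAE | Excluded from outcomes until after day 14 |
| Length of stay | Yes | Covariate screen at p < 0.1 only |
| Oxygen days | Yes | None |

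Length of stay runs past randomisation, so treatment could affect it. If it differed between arms at p < 0.1, VII.A would enter it in a stepwise Cox model for wheeze. It would be adjusted for, not reported as a result.

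**2. Dilution from counting only attributed events**

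Inputs: 100 per arm (up to 200 infants, 1:1; sections V.A and VII.B.1) and two-sided 0.05 (VII.B.1, stated for the primary outcome and assumed here). The all-cause rates p0 and p1, and the share q of events attributed to drug, are assumptions. Blinding makes one q for both arms reasonable. The counted rates become q·p0 and q·p1.

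Power = Φ{[|d| − 1.96·√(2p̄(1−p̄)/n)] / √[(a(1−a) + b(1−b))/n]}, where a = q·p0, b = q·p1, d = b − a and p̄ = (a+b)/2.

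For 10% v 25% with q = 1: p̄ = 0.175 and the standard errors are 0.0537 and 0.0527, so (0.15 − 0.1053)/0.0527 = 0.85 and power is 0.80.

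| q | 10% v 25% counted as | Power | 20% v 40% counted as | Power |
|---|---|---|---|---|
| 1 | 10 v 25 | 0.80 | 20 v 40 | 0.88 |
| 0.5 | 5 v 12.5 | 0.47 | 10 v 20 | 0.51 |
| 0.25 | 2.5 v 6.25 | 0.25 | 5 v 10 | 0.27 |
| 0.1 | 1 v 2.5 | 0.12 | 2 v 4 | 0.13 |

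At 94 per arm the 10% v 25% column reads 0.78, 0.44, 0.24 and 0.12. The visible risk difference shrinks in proportion to q: 15 points becomes 7.5 at q = 0.5.

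**3. What an all-cause comparison can deliver**

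Half-width of the 95% interval for a risk difference with rate p in both arms = 1.96·√(2p(1−p)/100).

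- p = 0.05 (assumed): 1.96·√0.00095 = 6.0 points
- p = 0.10 (assumed): 1.96·√0.0018 = 8.3 points
- p = 0.375, the pilot gastrointestinal rate, (7 + 8)/40: 1.96·√0.0046875 = 13.4 points

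For 80% power at 100 per arm, assumed placebo rates of 5, 10, 20, 30 and 40% need azithromycin rates of 17.4, 25.0, 37.9, 49.3 and 59.7%. That is an excess of about 12 to 20 points.

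The pilot does not settle the matter. With 7 v 8 gastrointestinal events and an assumed 19 or 20 infants per arm, Fisher's p is between about 0.75 and 1.0. At 20 per arm the difference is −5 points, with half-width 1.96·√(0.35·0.65/20 + 0.40·0.60/20) = 30 points.

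**The case against.** A reader might infer that early harm is never compared between arms, or that the relatedness definitions keep common infant events out of the safety outcome. The documents support neither.

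- Section VII.A tests the listed covariates between groups, and these include length of stay and in-hospital antibiotic use.
- *Possibly related* is open to common events and to events the illness could explain. Item f does not exclude that grade, and Management of SAEs (VI.B.2) treats all three related grades alike.
- The pilot's gastrointestinal events, which were common, were reported by arm (II.C, V.P.1).
- Calling worsening bronchiolitis expected (V.P, V.Q.6) does not exempt it from collection or from a relatedness judgment.
- All AEs go to the DSMB (VI), which reviews safety events. Its charter is not included, so by-arm review can be neither asserted nor ruled out.
- Respiratory hospitalizations and ED visits are exploratory outcomes after day 14 (V.F.3, items f and g).
- Attribution is blinded and is not confined to one person, so misjudgment should dilute a difference without favoring an arm.

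All of this stands, and it narrows the point. It does not supply the missing analysis. A covariate screen is not a safety result, DSMB review is not a pre-specified reported comparison, and events judged unrelated still enter no between-arm analysis. It is also fair that an all-cause comparison of this size detects only large excesses; its value is an unfiltered estimate with an honest interval.

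**Conclusion.** The point holds in limited form. The only clinical safety outcome and hypothesis are restricted to events attributed to drug, and no between-arm comparison of all-cause AEs or SAEs is pre-specified, including for days 1-14. The grades that count are not named, and no method is given even for the attributed rates.

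The size depends on the unknown share of true excess events that investigators attribute to drug. If half are attributed, power for 10% v 25% falls from 0.80 to 0.47; if a quarter, to 0.25. Those rates and shares are assumptions, since the documents give none. A finding of no difference, with no margin and on a diluted count, would be weak reassurance. It would not be evidence that harm was concealed, and the documents give no sign of attribution that differs by arm.

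Item f and section VI also use *severe*, which VI.B.2 defines as a severity grade, where the *serious* of VI.B.1 seems meant. This is mainly editorial, but it leaves the second half of item f open to two readings.

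**What to change.** 1. Restate item f and hypothesis 3 as all AEs and all serious AEs by randomised arm, regardless of attribution, for days 1-14 and from randomisation to Phone Call 1. Give the number of infants with an event, the risk difference and its 95% confidence interval.
2. Show respiratory worsening as its own category, taken from AE and SAE reports. ICU transfer and ventilation are not on the discharge recording list in V.E.2, so check how completely those reports capture them.
3. Report post-randomisation length of stay and oxygen days by arm as safety results. If oxygen is held only as a whole-stay count, the part before randomisation adds noise but, on average, no bias.
4. Keep attributed events as a supportive table, defined as possibly, probably or definitely related.
5. Write *serious* wherever the VI.B.1 definition is meant.

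The relatedness definitions need no change. Once all-cause rates lead they carry little weight, and Appendix 2 says treatment ended in spring 2019, so new definitions would mean re-grading recorded events. The change should be dated and made before anyone sees safety data by arm.

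The cost is a few tables, mostly from data already collected. Rates will look higher in both arms than attributed rates would, and the intervals will be wide, which the report should say.
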